**Title of the Research Project**

Evaluation of oral stereognosis in completely edentulous patients with maxillary tori.

**Introduction**

Stereognosis has been defined as the appreciation of the form of objects by manual palpation without the use of eye-sight. The term was introduced by H. Hoffmann in 1883. Whilst this definition holds good for the manual exploration of objects, it is also possible to extend the tactile perception of objects intraorally which is referred as Oral stereognosis (OS). It was first introduced by Berry and Mahood in 1966. Oral Stereognostic tests are performed using test specimens intraorally to determine the extent to which patients are able to distinguish shapes and surface structures. The OS testing is an indicator of overall sensory ability of the patient as the intraoral tactile sensation is conveyed through various cranial nerves including of trigeminal nerve, hypoglossal nerve and glossopharyngeal nerve.

Various studies have been designed to assess the oral stereognosis ability (OSA) by using a variety of test pieces with different shapes, materials, sizes, etc. with the objects kept away from patient's eyesight in order to evaluate the ability of patients to distinguish the shape and form of the test pieces. Several studies has proved that OSA decreases with age and completely edentulous patient had lower OSA when compared to dentate patients. The level of oral stereognostic score demonstrated a definite relationship with denture performance, that is patients with poor stereognostic ability appeared more satisfied with their complete denture prosthesis than did those with better stereognostic ability. Thus, evaluating OSA in edentulous patients who require rehabilitation with complete denture prosthesis may provide useful information about the sensory abilities of edentulous patients and aid in interpreting the role of adaptation and adjustment to the complete denture prosthesis.

OSA was even evaluated in patients with palatal anomaly like cleft lip and palate where the palatal hard and soft tissues are compromised. OS levels of denture wearers with cleft lip and palate were lower than those observed in edentulous subjects without clefts. However, there are no studies evaluating the effect of palatal tori on OSA. Torus palatinus (TP) are commonly found along the midline of the hard palate at the junction of the intermaxillary suture and the transverse palatine suture. Patients with TP may experience trauma or ulceration when masticating hard and sharp food since the soft tissue covering the bony protuberances is reported to be thinner than the surrounding mucosa. In addition, speech difficulties due to limited tongue movement, food lodgement resulting in malodour, difficulty in recording oral impressions and seating of dentures are the common problems. The prevalence of TP in Malaysian population was found to range between 12% to 65%. Hence, it is clear that Malaysian population carry a significant prevalence of TP and its effect on OSA has not been studied and this has been taken into consideration while designing this study. Thus, this research is designed to achieve a better understanding of the oral stereognosis in completely edentulous patients with maxillary tori.

### **Aim and Objective**

**Aim :** To evaluate the oral stereognostic ability in completely edentulous patient with maxillary tori.

**Objective :**

1. To compare the oral stereognostic ability of the completely edentulous patient with maxillary tori and patient without maxillary tori.
2. To compare the time duration taken for oral stereognosis of the completely edentulous patients with and without maxillary tori.

### **Background of the study**

Mantecchini et al (1998) evaluated oral stereognosis in edentulous subjects rehabilitated with complete removable dentures. Stereognosis was evaluated with and without the denture in place. The results showed that the older subjects had poorer stereognostic ability than the younger ones, whereas the duration of edentulism appeared not to influence this ability. The presence of a correct prosthetic rehabilitation appeared to improve stereognostic ability. Subjects with poorer stereognostic ability appeared more satisfied with their rehabilitation than did those with better stereognostic ability.

Pedreira A et al (2004) evaluated oral stereognosis in dentate and edentulous subjects with and without cleft lip and palate before and after chewing. The results demonstrated that oral stereognosis levels of dentate subjects were higher than those observed in edentulous subjects. Oral stereognosis levels of denture wearers with cleft lip and palate were lower than those observed in edentulous subjects without clefts. Chewing did not influence the oral stereognosis levels in edentulous patients.

Meenakshi S et al (2014) evaluated the oral stereognostic ability after rehabilitating patients with complete dentures and concluded that covering the palatal mucosa with a denture does not reduce oral stereognostic ability. Oral stereognostic test is a reliable test to measure patients' oral stereognostic perception which would enable the patient to appreciate the functional limitations of the denture.

Bakhtiyari J et al (2014) evaluated oral stereognostic ability and response time in children with cleft palate and normal children and showed that there was a significant difference between oral stereognosis and response time of children with cleft palate and that of normal

children ( $P < 0.05$ ) The results can be used for developing intervention programs for children with cleft palate in the early years of their lives.

Jin-Hyuck Park (2016) assessed the changes in oral stereognosis of healthy adults by age. This study investigated oral stereognosis in 184 healthy adults with normal eating and swallowing function. Results showed that oral stereognosis ability differ in age of the subjects and test pieces employed to test the OSA. The younger age group scored higher with short response time comparing to the older age group except for comparison between 20s and 30s age groups suggesting that aging negatively impacts in OSA in terms of speed in which sensory information is responded. Response time was negative correlated with test scores ( $r = -0.956$ ,  $P < 0.001$ ) and these proved that OSA decreases with age.

### **Materials and Methods**

Study will be conducted at Faculty of Dentistry SEGi Oral Health Center to evaluate oral stereognosis in completely edentulous patients with maxillary tori.

#### **Subject**

Inclusion Criteria :

- Complete edentulous patient with maxillary tori and without maxillary tori
- Complete edentulous patient who give consent and is willing to participate

Exclusion Criteria:

[figure not shown]
- Patients with swallow and mastication dysfunction
- Patients with cognitive disturbances
- Uncooperative patients.
- Patients with oral lesions, pathologies and TMJ disorders.

- Patients with systemic diseases
- Patients allergic to acrylic resin

The study group will comprise of 20 completely edentulous patients with maxillary tori and 20 completely edentulous patients without maxillary tori who are willing to participate in this study. The patients who fulfill the above mentioned inclusion and exclusion criteria would be conveniently selected from among outpatients of the SEGi Oral Health Centre. Informed consent will be obtained from each patient following sufficient explanation of purpose and contents of the research.

#### *Fabrication of test samples*

The 6 test pieces were selected from the 20 shapes of test pieces from National Institute of Dental Research (figure 1). The test pieces comprises 6 shaped form which include circle, eclipse, square, rectangular, triangle and star shaped with 13mm length and 2mm thickness. 2mm stainless steel wire will be used to fabricate as the test pieces mould. After fabrication of the test piece moulds by the stainless steel wire, the mould will be stamp on 2mm thickness of light cured acrylic resin, followed by curing of the resin for 30 seconds in light cure chamber. The test samples would be trimmed and polished to meet the standardized measurements. A total of 240 test sample (6 samples for each patient) for 20 completely edentulous patients with maxillary tori and 20 completely edentulous patients without tori will be made for this study. The test pieces will attached with dental floss. The attaching dental floss would prevent any accidentally aspiration of the test pieces.

**Fig. 1** The 20 shapes of the test pieces.

**Fig. 2** 6 test pieces shape that are chosen

#### Assessment of oral stereognostic test

The OSA test will be conducted in Segi Oral Health Centre under quiet condition. All patients will be seated comfortably in upright position on dental chair. All the test pieces will be kept out of sight of patient before and during the test. Test pieces will be placed intraorally and patients will be instructed to identify the shape of test pieces with their tongue and palate. A visual representation chart of all 6 shaped forms will be provided to patient for identification purpose. Patients will be asked to identify the correct shape form by pointing out on the

corresponding shape form on the chart. There will be no trial test held to avoid learning effect. The 6 test pieces will be presented randomly to the patients and correct answer will not be informed to the patients during the OSA.

The duration time for recognition of each shaped form for each patient will be noted and answers will be recorded on an OSA evaluation form. A correct answer will be recorded as one point and incorrect answer is zero point. A full 6 points will be scored if all answers were correct. The response time and the OSA scores will be recorded. The response time will be the time between the placements of test piece in the oral cavity until the identification of the test.

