### **Statistical analysis plan**

The data collection will include the time duration and OSA scores for recognition of each shaped form and the answers recorded on an OSA evaluation form. All data analyses will be conducted using SPSS version 22. Descriptive statistic will be used to analyse the mean and standard deviation of the OSA test scores and the response time for answering. Analysis of variants (ANOVA) will be applied to compare the test scores and response time among the completely edentulous patient with maxillary tori and completely edentulous patient without maxillary tori. Spearman's rank correlation coefficient would be used to investigate the relationship between response time and OSA test score.

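### Does naming the timed variable both recognition time and answering time leave the Objective 2 comparison ill-defined?

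*Combined protocol and SAP*

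**What the plan says.** Objective 2 is "To compare the time duration taken for oral stereognosis of the completely edentulous patients with and without maxillary tori". It does not mention correct answers.

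The section Assessment of oral stereognostic test refers to time twice. On what is recorded: "The duration time for recognition of each shaped form for each patient will be noted". As a definition: "The response time will be the time between the placements of test piece in the oral cavity until the identification of the test". The same section explains how identification happens: "Patients will be asked to identify the correct shape form by pointing out on the" matching picture on a chart of the six shapes. Answers score one or zero, and the patient is not told which was right.

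The Statistical analysis plan opens with the data to be collected, "the time duration and OSA scores for recognition of each shaped form". It then plans to describe "the mean and standard deviation of the OSA test scores and the response time for answering". The ANOVA between groups and the Spearman correlation with the score are both specified on response time.

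**The concern.** Two names for one variable invite two readings. Recognition suggests that the patient got the shape right; answering does not. The plan expects wrong answers, since it scores them zero, and it never says in words that their times count. The Background of the study adds to the worry. In summarising a cited ageing study it says that "aging negatively impacts in OSA in terms of speed in which sensory information is responded", which could lead a reader to take time as a measure of sensory speed.

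Time is one of only two objectives. The other asks whether the groups differ in accuracy, and that is one of the conditions under which the two readings separate. If the tori group made more errors and errors were slow, a longer mean time might be reported as slower recognition when it reflects more wrong answers. An undefined variable would also let an analyst choose between the readings after seeing the data.

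**Working it through.** **Which reading do the documents support?** Three points settle it.

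1. The definition runs the clock from placement to identification, and identification is the act of pointing. As the patient gets no feedback, the clock cannot run on until a correct answer is reached. It stops at whatever answer is given.
2. A time is noted for every shape and every patient: 6 × (20 + 20) = 240 timed answers. Only the all-answer reading fills all 240.
3. The Statistical analysis plan attaches the words for recognition to the OSA scores as well as to the times. Those scores include zeros, so the word names the task and not success at it.

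The ANOVA and the Spearman correlation carry no restriction to correct answers. The correlation needs a time for each patient whatever the score, and under a correct-only reading a patient scoring 0 would have none. If the six answers are independent with accuracy q, the chance of scoring 0 is (1 − q)^6:

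- q = 1/6 (pure guessing): (5/6)^6 = 0.335
- q = 0.5: 0.5^6 = 0.016
- q = 0.6: 0.4^6 = 0.004

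**How far apart could the readings be?** The plan states no figure to reproduce, so every input here is an assumption. Let correct answers take Tc and wrong answers Tw in both groups, with accuracies p1 (more accurate group) and p2 (less accurate group).

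- Mean time to answer in a group = p·Tc + (1 − p)·Tw
- Less accurate minus more accurate = (p1 − p2)·(Tw − Tc)
- The difference among correct answers alone is 0 by construction.

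With Tc = 10 s, p1 = 0.8 and p2 = 0.6:

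| Tw (s) | 80% group (s) | 60% group (s) | Difference (s) |
|---|---|---|---|
| 5 | 9 | 8 | -1 |
| 10 | 10 | 10 | 0 |
| 15 | 11 | 12 | +1 |
| 20 | 12 | 14 | +2 |

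At a 10-point accuracy gap the same values of Tw give half of each difference, -0.5 to +1 s. The gap vanishes if accuracies are equal or if wrong answers take as long as right ones.

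**What does the gap mean?** In each row with a non-zero difference, time to answer really does differ between the groups. An ANOVA that detects it is not giving a false positive for the planned comparison. It would mislead only as a test of speed of correct recognition, a quantity that neither the objectives nor the analysis section names.

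**The case for a change.** The strongest case for a change is that the effect could be large and that the remedy is nearly free. In simulations with 20 per group, six pieces, assumed log-normal times and equal speed on correct answers, the all-answer ANOVA rejected in 28% of studies at 80% against 60% accuracy when wrong answers took 2.5 times as long. The Spearman analysis is affected even without a group difference. At 70% accuracy in both groups, with correct-answer speed unrelated to ability, the mean correlation between time and score was -0.41 when wrong answers took twice as long, and it was significant in 78% of studies. Time and correctness per piece are already recorded, so a table of times by correctness would need no new data.

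Part of this stands. Neither result, if it appeared, would by itself show slower correct recognition, and a careful report would not say so. One term used throughout would also be tidier.

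The rest does not lead to a change:

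- The figures depend on the assumed gap and time ratio. At 75% against 65% accuracy the rejection rate is 5 to 11% across wrong-to-right time ratios of 0.5 to 2.5.
- Restricting to correct answers brings its own bias. In a simulation where harder trials were both slower and more often wrong, the correct-only comparison rejected in 7 to 13% of studies with no true difference, and a true log-difference of 0.30 shrank to between 0.21 and 0.24. All-answer time stayed near 5% and 0.30.
- The worry about choosing a reading after the fact needs a correct-only analysis, and the documents contain none.
- The phrase in the Background describes the speed of responding in someone else's study, which agrees with time to answer.

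**Conclusion.** The concern does not call for a change. The naming is loose, but the variable is defined once and analysed under one name, and the procedure leaves one workable reading: time from placement until the patient points to a shape, right or wrong. That this includes wrong answers is an inference from the pointing response, the lack of feedback, the timing of every piece and the unrestricted analyses. It is an inference any analyst holding the evaluation forms would make.

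Following the plan as written gives a sound comparison for Objective 2. The possible distance from speed of correct recognition, -1 to +2 s in the worked example, rests wholly on assumed accuracies and times, and it is measured against a quantity the plan does not claim to estimate. The sample size, the score endpoint and the choice of test are unaffected. A table of times by correctness would be an optional extra in the report.

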### **Statistical analysis plan**

The data collection will include the time duration and OSA scores for recognition of each shaped form and the answers recorded on an OSA evaluation form. All data analyses will be conducted using SPSS version 22. Descriptive statistic will be used to analyse the mean and standard deviation of the OSA test scores and the response time for answering. Analysis of variants (ANOVA) will be applied to compare the test scores and response time among the completely edentulous patient with maxillary tori and completely edentulous patient without maxillary tori. Spearman's rank correlation coefficient would be used to investigate the relationship between response time and OSA test score.

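### Unmatched convenience groups are compared with no age term, and age is not listed for collection, although the protocol says stereognosis declines with age

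*Combined protocol and SAP*

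**What the plan says.** **Selection.** Under Subject (Materials and Methods), 20 completely edentulous patients with maxillary tori and 20 without "would be conveniently selected from among outpatients of the SEGi Oral Health Centre". The readable inclusion and exclusion criteria contain no age range, matching or stratification. An image is missing inside the exclusion list.

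**Data.** The Statistical analysis plan says "The data collection will include the time duration and OSA scores for recognition of each shaped form", together with the answers on the evaluation form. Age is not named. The form itself is not shown.

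**Analysis.** "Analysis of variants (ANOVA) will be applied to compare the test scores and response time among the completely edentulous patient with maxillary tori" and the group without tori. No covariate is given. The only other inferential analysis is a Spearman correlation of response time with score, and descriptive statistics are planned only for those two outcomes.

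**Age.** The Introduction says "Several studies has proved that OSA decreases with age". The Background reports, from edentulous subjects rehabilitated with complete dentures, "The results showed that the older subjects had poorer stereognostic ability than the younger ones". From a study of healthy adults it adds that "aging negatively impacts in OSA in terms of speed in which sensory information is responded".

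**The concern.** Both objectives compare the two groups, one on score and one on time, and the Introduction frames the question as an effect of the torus: "Malaysian population carry a significant prevalence of TP and its effect on OSA has not been studied". The groups are not randomised, and the protocol itself treats both outcomes as age-dependent. An ANOVA with group as its only term cannot separate a torus difference from an age difference.

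The error can run either way. An older tori group could produce a false deficit, and a younger one could mask a real deficit. If age is not recorded, no reader can check for this afterwards.

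**Working it through.** **What can be reproduced.** The documents give no alpha, power, effect size or SD, so the 20 per group cannot be re-derived. The one figure that can be checked agrees: 6 pieces × (20 + 20) patients = 240 test samples.

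**Inputs.** From the documents: n = 20 per group. Assumed: two-sided alpha 0.05; normal outcomes, linear in age, with within-group SD 1; absolute within-group correlation of age with outcome r = 0.2 to 0.7; difference in mean age g = 0.25 to 0.8 age SDs. The correlation of -0.956 quoted in the Background relates response time to score, not to age, and is not used.

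**False-positive rate with no true torus effect.** A two-group ANOVA is a two-sample t-test with 38 df.

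- Spurious standardised difference: d = r × g.
- Noncentrality: d × √(n/2) = r × g × √10.
- Example, r = 0.5 and g = 0.5: d = 0.25, noncentrality 0.25 × 3.162 = 0.791, rejection rate 12.0%.

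| Age gap (SD) | r = 0.2 | r = 0.3 | r = 0.5 | r = 0.7 |
|---|---|---|---|---|
| 0.25 | 5.3% | 5.6% | 6.7% | 8.4% |
| 0.5 | 6.1% | 7.5% | 12.0% | 19.0% |
| 0.8 | 7.8% | 11.5% | 23.4% | 40.8% |

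ANCOVA with group and age (37 df, 100,000 simulated studies per cell) rejects in 4.9% to 5.1% of studies in every cell.

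**Masking.** Take a true deficit of 0.8 SD and a tori group 0.5 SD younger. The unadjusted noncentrality is (0.8 − 0.5r) × √10. At r = 0.5 this is 0.55 × 3.162 = 1.739. With no age gap it is 0.8 × 3.162 = 2.530, and power is 69.3%.

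| Power | r = 0.2 | r = 0.3 | r = 0.5 | r = 0.7 |
|---|---|---|---|---|
| Unadjusted | 57.8% | 51.7% | 39.6% | 28.4% |
| ANCOVA with age | 67.0% | 69.4% | 77.4% | 90.8% |

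**Price of adjusting.** For a true 0.8 SD effect, adjusted power at age gaps of 0, 0.5 and 0.8 SD is 80%, 77% and 74% when r = 0.5, and 70%, 67% and 63% when r = 0.2. The unadjusted test with no gap has 69%.

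**Chance gaps.** If both groups came from populations of the same age, the difference in mean age would have standard error √(2/20) = 0.316 SD. It would exceed 0.5 SD in either direction with probability 2 × [1 − Φ(0.5/0.316)] = 11.4%. Such gaps leave the long-run 5% error rate intact but distort the particular study in which they occur.

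**The case against.** **No stated link between torus and age.** Confounding needs age to be related to torus status as well as to the outcome. The documents give only the prevalence and site of tori, and both groups come from one clinic under the same criteria. This stands: the plan is exposed to bias, but bias is not demonstrated.

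**Incomplete text.** The data list is not worded as exhaustive, the evaluation form is not shown, and the missing image could hold a further criterion. Age may therefore be recorded. This also stands, but recording age would not by itself repair an analysis with no age term and no plan to report age by group.

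**Thin evidence on size.** Only one cited study covers edentulous subjects, with no effect size given, and the support for slower responses comes from healthy adults. At the low end (r = 0.2, gap 0.25 SD) the inflation is negligible, and the 41% corner needs values that no section supports. This is why a range is shown.

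**Normality.** The score is an integer from 0 to 6, and times cannot be negative. With assumed 0 to 6 scores or lognormal times, the unadjusted rate at r = 0.5 and gap 0.5 SD fell from 12.0% to between about 9% and 11.6%, depending on the shape assumed. ANCOVA gave about 3.5% to 5%. The percentages are approximate, but the direction does not change.

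**Objectives ask only for a comparison.** An unadjusted ANOVA does compare the groups. It does not answer the question of a torus effect raised in the Introduction.

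**Conclusion.** The concern holds. The plan leaves a factor that it describes as affecting both outcomes uncontrolled in a non-randomised comparison. Under the assumptions above, a moderate case (r = 0.5, age gap 0.5 SD) raises the false-positive rate from 5% to about 12%. With the tori group younger by the same amount, power for a 0.8 SD deficit falls from 69% to 40%. Across the range considered, the false-positive rate runs from 5.3% to 41%. These figures depend on an assumed correlation and age gap, and the harm arises only if the groups do differ in age. The case for adjustment is protection against bias; at weak correlations there is little or no gain in power. It is a cheap improvement, not a fatal flaw.

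**What to change.** 1. Add age to the evaluation form and report it by group.
2. In the Statistical analysis plan, make ANCOVA with group and age the main comparison for both score and response time, and keep the unadjusted ANOVA as secondary.
3. Optional: where feasible, frequency-match the patients without tori to the tori group by age band.
4. Optional: record current complete-denture use and describe it by group, but use it only in a sensitivity analysis. The Introduction says of tori that "difficulty in recording oral impressions and seating of dentures are the common problems", so denture use may be a consequence of the torus, and adjusting for it could remove part of the effect under study.

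The first two changes cost one form item, one sentence and one degree of freedom. In the least favourable case shown (r = 0.2, age gap 0.8 SD), adjusted power is 63%, about 6 points below the 69% of the unadjusted test with no gap. Denture use would add a second form item. Matching could slow selection; by how much is unknown, since the prevalence quoted in the Introduction runs from 12% to 65%.

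### Does the plan's silence on how each patient's six response times enter the ANOVA endanger the comparison of times between groups?

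*Combined protocol and SAP*

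**What the plan says.** All references are to the combined protocol and SAP.

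- **Objective.** The second objective is "To compare the time duration taken for oral stereognosis of the completely edentulous patients with and without maxillary tori". The comparison is between groups of patients.
- **Subject.** The groups are "20 completely edentulous patients with maxillary tori and 20 completely edentulous patients without maxillary tori".
- **Assessment of oral stereognostic test.** Time is defined per piece: "The response time will be the time between the placements of test piece in the oral cavity until the identification of the test". With six pieces, each patient has six times. The score is built up to the patient: one point per correct answer, and "A full 6 points will be scored if all answers were correct".
- **Statistical analysis plan.** The data sentence is per shape: "The data collection will include the time duration and OSA scores for recognition of each shaped form". The descriptive sentence reads "Descriptive statistic will be used to analyse the mean and standard deviation of the OSA test scores and the response time for answering". The inferential sentence reads "Analysis of variants (ANOVA) will be applied to compare the test scores and response time", between the group with tori and the group without. A Spearman correlation then relates response time to the test score.

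No section defines a patient-level time, names the unit of analysis, or gives a significance level.

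**The concern.** The score has a stated patient total and the time does not. Because the data sentence speaks of each shape, an analyst could defend three data layouts: one time per patient (40 values), six separate shape comparisons, or one ANOVA on all 6 × 40 = 240 times. The second multiplies tests. The third treats six times from the same mouth as independent.

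Background of the study adds a temptation. It cites a study in which "oral stereognosis ability differ in age of the subjects and test pieces employed to test the OSA", so looking shape by shape would seem natural. If the layout were chosen after the data were seen, the verdict on the second objective could depend on that choice. The reported SD is also open, since the SD of single times is larger than the SD of patient means.

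**Working it through.** **Inputs from the documents.** 20 patients per group (Subject); 6 pieces per patient (Fabrication of test samples). The count of 240 there is reproduced exactly: 6 × (20 + 20) = 240. It counts fabricated test pieces, not rows of an analysis.

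**Assumed, not in the documents.** Two-sided 5% level. Within-patient correlation of times ρ = 0.1, 0.3 or 0.5. Normal times, with a lognormal check. v, the variance between shape means divided by the variance of times within a shape, from 0 to 1.

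**Step 1. Which layout does the text support?**

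| Text | Points to |
|---|---|
| Objective compares patients with and without tori | one value per patient |
| Score is a 0-6 total per patient | one value per patient |
| Spearman pairs time with that score | one time per patient |
| Data sentence refers to each shape | how data are recorded, not how they are tested |

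Nothing describes an ANOVA on 240 rows. Nothing says the second objective is met if any single shape differs.

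**Step 2. One value per patient.** In 100,000 simulated null trials per setting, the ANOVA on patient means rejected in 5.0% at each ρ with normal times, and in 4.8-4.9% with lognormal times. Whether the mean or the total is used does not matter when all six times are present. The total is 6 × the mean, so the F ratio is unchanged, and so are the ranks used by Spearman.

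**Step 3. Six uncorrected shape tests, claiming a difference if any is significant.** With independent times the rate is 1 − 0.95⁶ = 26.5%. Correlation within patients lowers it: 26.1%, 24.6% and 21.1% at ρ = 0.1, 0.3 and 0.5 (lognormal 24.6%, 22.9%, 20.2%). This is a family-wise rate; each single test stays at its nominal 5%.

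**Step 4. 240 pooled times.** A group mean of 120 times has variance proportional to 1 + 5ρ, while the pooled analysis assumes 1 + v. The error is therefore about

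2 × [1 − Φ(1.96 × √((1 + v)/(1 + 5ρ)))].

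With v = 0:
- ρ = 0.1: 1.96/√1.5 = 1.60, giving 11.0% (simulated 11.0%)
- ρ = 0.3: 1.96/√2.5 = 1.24, giving 21.5% (simulated 21.8%)
- ρ = 0.5: 1.96/√3.5 = 1.05, giving 29.5% (simulated 30.2%)

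If shape is ignored and shapes differ, the error falls. At ρ = 0.1 the simulated rate is 7.4% for v = 0.25, 4.0% for v = 0.65 and 2.3% for v = 1. At ρ = 0.5 the corresponding rates are 24.5%, 18.0% and 13.9%. A rate near or below 5% thus needs sizeable shape differences as well as a low ρ.

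**Step 5. The reported SD.** The SD of patient means divided by the SD of single times is √(((1 + 5ρ)/6)/(1 + v)). With v = 0 this is √(1.5/6) = 0.50 at ρ = 0.1 and √(3.5/6) = 0.76 at ρ = 0.5.

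**The case for a change.** The strongest case for amending the plan is that the analysis section is one short paragraph, that it builds a patient total for the score but none for time, and that one clause would settle the matter before data are seen. With no true difference, the three layouts fail to agree in about 22-29% of simulated trials, for ρ from 0.1 to 0.5 and shape means whose SD is 0 to 0.78 of the within-shape SD. The SD question also arises even if nobody pools.

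Part of this stands. The summary of the six times is not written down, and a reader of the results will need to be told what the SD describes. If some times were missing, mean and total would no longer give the same test.

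The rest carries less weight. The disagreement rate is close to the any-of-six rate of 21-26% in step 3, and it depends on counting two layouts that the plan never states as equal alternatives. The shape-by-shape layout rests on a sentence about data collection, and its error rate needs a decision rule that appears nowhere in the document. The documents raise no expectation of missing times. A clause would record what the plan already implies, and a label in the results table settles the SD. A mixed model or a by-shape table would be additions rather than repairs to a stated rule.

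**Conclusion.** The omission is real but harmless on the natural reading, so no change to the plan is needed. The objective, the patient-level score and the Spearman pairing lead an analyst to one time per patient, and the planned mean and SD make the mean the obvious summary. That analysis holds 5.0% under an assumed two-sided 5% level, for ρ from 0.1 to 0.5, and 4.8-4.9% with lognormal times.

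The inflated figures (21-26% family-wise for six shape tests; 11-30% for pooling with equal shape means) belong to analyses that the documents do not describe. They rest on an assumed ρ, and the pooled figure also on an assumed absence of shape differences, so they do not measure a defect in this plan. This is missing detail that a competent analyst fills sensibly. An author who wishes to note that the patient's mean time and 0-6 total are the values analysed may do so, but the planned result does not depend on it.
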